9.2 Definitions of Adverse Event Severity and Relationship to Study Drug

9.2.1 Severity

The severity, or intensity, of an AE refers to the extent to which an AE affects the patient's daily activities. Adverse event severity will be evaluated using the criteria in [Table 10](#).

Table 10 Definitions of AE Severity Criteria

| AE Severity | Definition |
|-----------------|---|
| Mild | Mild; asymptomatic or mild symptoms; clinical or diagnostic observations only; intervention not indicated. |
| Moderate | Moderate; of sufficient severity to make the patient uncomfortable; minimal, local, or noninvasive intervention indicated. |
| Severe | Severe or medically significant, of sufficient severity to cause the patient severe discomfort; may cause cessation of treatment; treatment of event symptoms/intervention may be required. |

Abbreviations: AE = adverse event;

Changes in the severity of an AE should be documented in the eCRF to allow an assessment of the duration of the event at each level of intensity.

9.2.2 Relationship to Study Drug

The Investigator's assessment of an AE's relationship to study treatment is part of the documentation process, but it is not a factor in determining what is or is not reported in the study. All AEs, regardless of relationship, will be recorded in the eCRF. In addition, SAEs will be reported to regulatory authorities as required by local regulation ([Section 9.3.4](#)).

The relationship or association of the study drug in causing or contributing to the AE will be characterized using the classification and criteria presented in [Table 11](#).

Table 11 Guidelines for Determining the Relationship (if any) Between Adverse Event and the Study Drug

| AE Relationship | Definition |
|-------------------------|--|
| Definite | This relationship suggests that a definite causal relationship exists between treatment administration and the AE, and that other conditions (concurrent illness, progression/expression of disease state, or concurrent medication reaction) do not appear to explain the event. The event reappears or worsens if the study treatment is re-administered. |
| Probable | This relationship suggests that a reasonable temporal sequence of the event with treatment administration exists and, based upon the known pharmacological action of the treatment, known or previously reported adverse reactions to the treatment or class of treatment, or judgment based on the Investigator's clinical experience, the association of the event with the study treatment seems likely. The event disappears or decreases on cessation of study treatment. |
| Possible | This relationship suggests that the study treatment caused or contributed to the AE, i.e., the event follows a reasonable temporal sequence from the time of treatment administration or follows a known response pattern to the study treatment, but could also have been produced by other factors. |
| Unlikely Related | This relationship suggests an improbable (but not impossible) association between the study medication and the reported event. |
| Not Related | This relationship suggests no association between the study treatment and the reported event. |

Abbreviations: AE = adverse event.

9.3 Serious Adverse Events

9.3.1 Serious Adverse Event Criteria

An SAE is defined as any event that results in death, is immediately life threatening, requires inpatient hospitalization or prolongation of existing hospitalization, results in persistent or significant disability/incapacity, or is a congenital anomaly. Important medical events that may not result in death, be life threatening, or require hospitalization may be considered SAEs when, based upon appropriate medical judgment, they may jeopardize the patient or may require medical or surgical intervention to prevent one of the outcomes listed in this definition.

Examples of such medical events include allergic bronchospasm requiring intensive treatment in an emergency room or at home, blood dyscrasias or convulsions that do not result in inpatient hospitalization, or the development of drug dependency or drug abuse. A life-threatening event does not include an AE that, had it occurred in a more severe form, might have caused death.

Serious AEs must be reported (Section 9.3.4) and will be followed through the follow-up visit. An SAE that occurs after the final follow-up visit need not be reported unless the Investigator or the Sponsor considers it related to study drug.

The Sponsor pharmacovigilance risk management physician will provide a Sponsor causality statement for all SAEs.

9.3.2 Suspected, Unexpected Serious Adverse Reaction

A suspected, unexpected, serious adverse reaction (SUSAR) is an SAE for which there is a reasonable possibility that the drug caused the event, and this SAE has not been previously identified as an expected/listed AE. If an investigational agent is early in development all SAEs may be considered unexpected. Later phase investigational agents may have an identified list of expected AEs. A list of expected AEs (if applicable) is provided in the current version of the Investigator's Brochure and is considered the Reference Safety Information (RSI) for the study. Generally, the indication for which a product is intended would not be on the list of expected AEs, but if it did occur, would not be considered "unexpected" for SUSAR reporting. As an example, a flare-up of symptoms consistent with the underlying disease under treatment that required hospitalization would constitute an SAE; however, the event would not be considered unexpected. An exception would be if the reporter believed that study drug worsened the underlying condition.

9.3.3 Serious Adverse Event Follow-up

Appropriate remedial measures should be taken by the Investigator using his/her best medical judgment to treat the SAE. These measures and the patient's response to these measures should be recorded. All SAEs regardless of relationship to study drug will be followed by the Investigator until resolution. Clinical, laboratory, and diagnostic measures should be employed by the Investigator, as needed, to adequately determine the etiology of the event.

9.3.4 Serious Adverse Event Reporting

9.3.4.1 Reporting Requirements

Any AE that meets SAE criteria (Section 9.3.1) must be reported to the Sponsor and/or designee immediately (i.e., within 24 hours) after the time site personnel first learn about the event. The SAE Report Form provided for the study must be used. Regardless of causality, all SAEs must be reported and will be collected and recorded from the time the patient/parent/legal guardian signs the ICF until completion of the final follow-up visit. All SAEs must also be recorded in the patient's source documentation and on the AE page of the patient's eCRF.

The initial report should include at least the following information:

- Study Number
- Patient's identification number

- Description of the event
- Date and time of onset of the event
- Seriousness criteria
- Causality assessment to study drug

If follow-up is obtained, or requested by the Sponsor and/or designee, the additional information should be e-mailed on an SAE Report Form to WAVE and/or designee, in a timely manner according to the procedures outlined above. Copies of discharge summaries, consultant reports, autopsy reports, and any other relevant documents may also be requested.

The Investigator will be responsible for reporting all SAEs to the Institutional Review Board (IRB) or Ethics Committee (EC). The Sponsor will be responsible for reporting to the regulatory authorities and Central Ethics Committees, as per local requirements.

9.3.4.2 *SAE Contact Information*

Serious adverse event contact information is provided in the [Study Identification Table](#).

9.4 Overdose

The study drugs are planned to be administered by trained study staff. Administration will be performed in accordance with the IB and instructions in a study-specific manual. Any incidence of overdose should be recorded as an SAE.

No clinical data are available regarding overdose with WVE-210201. As with any agent, if overdose occurs, general supportive measures and close observation should be instituted. Misuse of the study drug for illegal purposes is not expected in this study as patients have no direct access to the study drugs.

10 PREGNANCIES

Not applicable.

11 STATISTICAL METHODS

11.1 Sample Size Determination

Approximately 150 patients are planned to be enrolled in this study. This study was designed to demonstrate the efficacy of WVE-210201 compared to placebo on a clinical endpoint, NSAA.

The sample size determination for the NSAA endpoint was based on the following assumptions:

- Two-sample t-test to test for statistical significance of treatment difference

- 1:1:2:2 placebo 3 mg/kg, placebo 4.5 mg/kg, WVE-210201 3 mg/kg, and WVE-210201 4.5 mg/kg randomization ratio
- Standard deviation of change in NSAA from baseline to 48 weeks⁵⁵ of 4.5
- Treatment difference of change in NSAA from baseline to 48 weeks of 3.0 between WVE-210201 and placebo
- Dropout rate of 10%
- Two-sided significance level of 5%

With these assumptions, a sample size of 150 patients provides 88% power to detect a difference of 3 in the change in NSAA from baseline to 48 weeks. The treatment difference of 3 was selected as it is equal to the average 1-year decline observed in longitudinal natural history studies^{55,56}.

The power of the dystrophin endpoint was based on the following assumptions:

- Two-sample t-test to test for statistical significance of treatment difference
- 150 patients randomized 1:1:2:2 placebo 3 mg/kg, placebo 4.5 mg/kg, WVE-210201 3 mg/kg, and WVE-210201 4.5 mg/kg
- Standard deviation of change in dystrophin protein level from baseline to 46 weeks of 3.0%
- Treatment difference of change in dystrophin protein level from baseline to 46 weeks of 4.0% between WVE 210201 and placebo
- Dropout rate of 10%
- Two-sided significance level of 5%

With these assumptions, the power is greater than 99% to detect a difference of 4% in the change in dystrophin level from baseline to 46 weeks.

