4.1.2 Double-blind Treatment Period

In the Double-blind Treatment Period, patients will receive weekly intravenous (IV) doses of either placebo or WVE-210201. Patients will be randomized in a 1:1:2:2 ratio to placebo 3 mg/kg, placebo 4.5 mg/kg, WVE-210201 3 mg/kg, and WVE-210201 4.5 mg/kg. Patients must be randomized within one day prior to their first dose. Safety and efficacy assessments will be performed over the course of study. All functional assessments, performance of upper limb (PUL), NSAA, myometry, timed function tests, and pulmonary function tests (peak flow rate [PFR], cough peak flow [CPF], and forced vital capacity [FVC]) and completion of the Pediatric Quality of Life questionnaires must be done pre-dose (on the dosing day or up to 24 hours prior to respective dosing day). The ActiMyo wearable device will also be given to patients, and activity data will be collected throughout the study at specified timepoints. To minimize the potential unblinding, functional assessments must be completed by an assessor not involved in administration of study drug or assessment and recording of AEs during the study. The same assessor should perform the functional assessments throughout the study for a given patient to minimize variability of assessments.

A second open muscle biopsy (deltoid) will be collected at 1 of 3 timepoints mentioned below:

- First 30 patients: Week 12
- Next 40 patients: Week 22
- Remaining patients: Week 46, 2 weeks prior to Week 48 visit.

The biopsy timing facilitates interim analyses of dystrophin; all biopsies will be used in the primary efficacy analysis. The open muscle biopsies will be collected to allow for adequate tissue quantity and quality for analysis of dystrophin-related study endpoints via Western blot analysis (dystrophin protein level), and other pharmacodynamic assessment methods (e.g., dystrophin localization by immunohistochemistry, exon skipping via RT-PCR).

In addition, pharmacokinetics of WVE-210201 will be determined. Immunogenicity analysis will also be performed.

Patients and parents will be asked to complete the quality of life questionnaires as applicable.

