11.3.2 Analyses of Efficacy Endpoints

11.3.2.1 Analysis of dystrophin protein level

A primary objective of this Phase 2/3 study is to evaluate the efficacy of WVE-210201 by assessing changes in dystrophin protein levels. Therefore, the primary efficacy endpoint for the United States and Other regions, as applicable, and the key secondary endpoint for the EU and Japan is the change in dystrophin protein level (% normal) from baseline. The treatment policy estimand, which assesses the effect of treatment initially assigned at baseline (regardless of adherence to the planned course of treatment), will be used. The analysis population will be the ITT population. The main estimator is a Bayesian analysis of covariance (ANCOVA). The model will include fixed effects for mean change from baseline in dystrophin levels at each time point for placebo and fixed effects for the increase or decrease in dystrophin compared to placebo for each treatment arm at each time point.

Let the change from baseline in dystrophin level at time point j for patient i be Y_{ij} , for $j = 1, 2, 3$ and $i = 1, \dots, n$. Time periods $j = 1, 2$, and 3 , refer to the post-baseline visits at 12, 22 and 46 weeks; each patient will have one Y_{ij} with either $j = 1, 2$, or 3 . The ANCOVA model is

$$Y_{ij} = \alpha_j + \theta_{t(i),j} + \epsilon_{ij};$$

$$\epsilon_{ij} \sim N(0, \sigma_{t(i),j}^2).$$

The $\alpha_j, j = 1, 2, 3$, parameters represent the mean change from baseline in dystrophin level at each time point for placebo-treated patients. For patient i , the treatment arm is labelled $t(i)$ with 0 for placebo, 1 for WVE-210201 3 mg/kg and 2 for WVE-210201 4.5 mg/kg. The effect of treatment T at time j is the parameter $\theta_{T,j}, T = 0, 1, 2$ and $j = 1, 2, 3$. For placebo, the effect is assumed to be 0 ($\theta_{0,j} = 0$). Thus, the treatment effect parameter for treatment T at time j represents the mean difference in the change from baseline in dystrophin at time j compared to placebo. The errors for the individual observations, ϵ_{ij} , are assumed independent and follow a normal distribution. The standard deviation, $\sigma_{T,j}, T = 0, 1, 2$ and $j = 1, 2, 3$, is specific to treatment arm and visit.

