Summaries of the posterior distribution for the treatment difference in dystrophin compared to placebo at each time point for each arm will be provided including the probability that each treatment is superior to placebo at each time point, $\Pr(\theta_{T,j} > 0)$, as well as mean and 95% credible intervals.

The dystrophin analysis will be supplemented with dystrophin data from the ongoing Open-label extension study to the Phase 1 trial (WVE-DMDX51-002). These results will be available at the time of the first dystrophin interim analysis.

Missing dystrophin data can result from intercurrent events which include discontinuation of the study and non-evaluable biopsies. Previous pivotal studies in DMD, including exon skipping therapies, have had low study discontinuation rates (e.g. 0.6% and 2.7%) so it is anticipated that missing data resulting from study discontinuation will be limited (^{57,58}). With the selected estimand, missing dystrophin results due to study discontinuation will be handled using baseline imputation. Non-evaluable dystrophin will be addressed using imputation under the assumption of missing-at-random (MAR). The regression method for monotone missing data will be used for the multiple imputation with baseline dystrophin as a covariate and imputation stratified by treatment arm.

There will be two interim dystrophin efficacy analyses and a final dystrophin efficacy analysis. The dystrophin treatment effects will be declared significant at the interim or final analyses using a gatekeeping strategy where the WVE-210201 4.5 mg/kg arm is assessed first and, if significant, the WVE-210201 3 mg/kg arm is assessed. To account for the three possible analyses of the dystrophin treatment effects, a Bonferroni-level adjustment will be applied. A one-sided, significance threshold of $1 - (0.025/3) = 0.991667$ will be used for the Bayesian posterior probability of superiority of each dose compared to placebo. If successful for WVE-

210210 4.5 mg/kg, the same threshold will be used for WVE-210210 3 mg/kg. Specifically, success will be declared for WVE-210201 4.5 mg/kg if

1. $\Pr(\theta_{2,1} > 0) > 0.991667$ at the first dystrophin interim analysis,
2. $\Pr(\theta_{2,2} > 0) > 0.991667$ at the second dystrophin interim analysis, or
3. $\Pr(\theta_{2,3} > 0) > 0.991667$ at the final dystrophin analysis.

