It is assumed that $\beta_0 = 0$ and the decline in NSAA per each 12-week period for a placebo patient in this study with average baseline covariates is modelled as $\beta_k, k = 1, \dots, 4$, with the sum of all β_k equal to the total decline over 48 weeks. Each β_k is assumed to be less than or equal to zero to ensure a monotonic decline.

For patient i , the treatment arm is labelled $t(i)$ with 0 for placebo, 1 for WVE-210201 3 mg/kg and 2 for WVE-210201 4.5 mg/kg. The disease rate ratio (DRR) for treatment T is the parameter $\exp(\theta_T), T = 0, 1, 2$. For a placebo-treated patient, the DRR is assumed to be 1 ($\theta_0 = 0$). Thus, the DRR parameter for treatment T represents the multiplicative change to the mean decline of a placebo-treated patient. If the DRR is less than 1, the rate of decline for treatment T is slower than placebo; the DRR value represents the proportional slowing of NSAA progression. For example, a DRR = 0.75 corresponds to a 25% slowing in the rate of NSAA progression. The WVE-210201 treatment arms will be pooled for the NSAA analysis and the restriction that $\theta_1 = \theta_2$ incorporated into the DPM. However, if the randomization to the WVE-210201 3 mg/kg arm is stopped after an interim analysis (Section 11.5), the WVE-210201 treatment arms will not be pooled. Summaries of the posterior distribution for the DRR ($\exp(\theta_T)$) for each arm will be provided including the probability that each treatment is superior to placebo, $Pr(\exp(\theta_T) < 1)$, as well the mean and 95% credible intervals for each DRR.

Patient-specific multiplicative random effects in the slope, $\exp(\eta_i), i = 1, \dots, n$, represent the patient-specific proportional increase or decrease in the rate of progression. Covariate effects are modelled as $\alpha_c, c = 1, \dots, C$, and account for explained variability in the rate of NSAA progression due to subject-specific baseline covariates.

Random data source effects to account for the between-source variability in NSAA progression rates are modelled as $\delta_{s(i)}$, where the source of each patient is labelled $s(i)$ with 0 for this study and 1:S for the historical data sources. These source effects account for the variability in the rate of progression of NSAA between placebo and historical controls in the different data sources that are not explained by baseline covariates. For a patient randomized in this study, the source effect is assumed to be 1 ($\delta_0 = 0$).

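### The power figures in Section 11.1 and the synopsis do not describe the planned tests: Week 46 dystrophin power is about 98% to 99%, slightly below the stated figure, and the NSAA 88% is for one dose against placebo, not the default pooled comparison

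*Combined protocol and SAP*

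**What the plan says.** Section 11.1 and the synopsis give two power statements, each based on a two-sample t-test with 10% dropout and two-sided 5%.

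- **NSAA.** With SD 4.5 and a difference of 3.0, "a sample size of 150 patients provides 88% power to detect a difference of 3 in the change in NSAA". The effect is described as lying between WVE-210201 and placebo, without saying whether that means one dose or both.
- **Dystrophin.** With 150 patients, SD 3.0% and a difference of 4.0%, "the power is greater than 99% to detect a difference of 4% in the change in dystrophin level from baseline to 46 weeks".

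The analysis sections describe different tests.

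- **NSAA (Section 11.3.2.2).** By default, "The WVE-210201 treatment arms will be pooled for the NSAA analysis". Only if randomization to 3 mg/kg is stopped does the plan say that "the WVE-210201 treatment arms will not be pooled". Missing or post-discontinuation NSAA values in treated patients are imputed by a control-based strategy.
- **Dystrophin (Section 11.3.2.1).** The model covers "post-baseline visits at 12, 22 and 46 weeks; each patient will have one" outcome, taken at one of those visits. Placebo mean and treatment effect are indexed by visit, and the residual SD "is specific to treatment arm and visit". The 4.5 mg/kg dose is tested first, at Week 12, Week 22 and Week 46 in turn. "To account for the three possible analyses of the dystrophin treatment effects, a Bonferroni-level adjustment will be applied", which sets the posterior threshold at 0.991667.
- **Who has a Week 46 biopsy (Section 11.5.1).** Patients 71 to 150, so 80 at most.
- **Section 4.1.2 and the synopsis** add that "all biopsies will be used in the primary efficacy analysis".

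**The concern.** Section 11.1 is where a reader looks for the power of the planned tests. For dystrophin, the primary endpoint in the United States, it uses a sample size and an alpha that the Week 46 test does not use. The sentence about all biopsies may be where the 150 came from, but under the stated model biopsies from Weeks 12 and 22 carry no information on the Week 46 effect.

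For NSAA, which drives the sample size, the arms compared are not named. A reader cannot tell whether 88% belongs to the default pooled test or to the single-dose comparison used if 3 mg/kg is dropped.

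The Week 46 figure also depends on full enrollment. An NSAA interim may stop enrollment before 150 (Section 11.5.2), and every patient not enrolled is then a lost Week 46 biopsy. Section 11.1 does not show this.

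**Working it through.** **Method.** Noncentral-t power for a two-sample t-test with equal SDs: ncp = d / (SD × √(1/n1 + 1/n2)), df = n1 + n2 − 2.

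**Numbers per group.** Under 1:1:2:2, 150 patients give 50 combined placebo, 50 at 3 mg/kg and 50 at 4.5 mg/kg. Removing 10% leaves 45 per group, or 90 with the doses pooled.

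**1. Reproducing the NSAA 88%** (d = 3, SD = 4.5, two-sided 5%)

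| Comparison | n | Power |
|---|---|---|
| One dose vs combined placebo, 10% removed | 45 vs 45 | 87.9% |
| Pooled doses vs combined placebo, 10% removed | 90 vs 45 | 95.2% |
| One dose vs its matched placebo, 10% removed | 45 vs 22.5 | 72.0% |
| One dose vs combined placebo, no dropout | 50 vs 50 | 91.0% |
| Pooled doses vs combined placebo, no dropout | 100 vs 50 | 96.9% |

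Only the first row matches: ncp = 3 / (4.5 × √(2/45)) = 3.16 on 88 df. That 88% means one dose against combined placebo is therefore an inference from the arithmetic. The document does not say so.

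**2. NSAA under the control-based rule.** Suppose 10% of treated patients are imputed at the placebo mean and all patients stay in the analysis, with SD unchanged. The effect becomes 0.9 × 3 = 2.7.

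- One dose, 50 vs 50: ncp = 2.7 / (4.5 × √(2/50)) = 3.00; power 84.4%.
- Pooled, 100 vs 50: ncp = 2.7 / (4.5 × √(1/100 + 1/50)) = 3.46; power 93.1%.

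The pooled figure also needs a 3-point effect in both doses. If 3 mg/kg gave 2 points, the average effect would be (3 + 2)/2 = 2.5 and pooled power 85.6% (90 vs 45, dropouts removed).

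**3. Reproducing the dystrophin figure** (d = 4, SD = 3, two-sided 5%). With 45 vs 45, ncp = 4 / (3 × √(2/45)) = 6.32; power is 99.999%, in line with the statement.

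**4. The planned Week 46 test.** Alpha is one-sided 0.025/3 = 0.00833. Eighty biopsies over three equal groups give 80/3 = 26.7 per group. Removing 10% leaves 72, or 24 per group.

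- 10% loss, 24 vs 24: ncp = 4 / (3 × √(2/24)) = 4.62 on 46 df; power 98.1%. A Welch simulation, closer to arm-specific variances, gives 98.2%.
- No loss, 26.7 vs 26.7: ncp = 4.87; power 99.0%.
- Baseline imputation instead of removal, 10% set to zero change in both arms: difference 0.9 × 4 = 3.6; variances 0.9 × 9 + 0.09 × 16 = 9.54 (active) and 0.9 × 9 = 8.1 (placebo); SE = √((9.54 + 8.1)/26.7) = 0.813; normal-approximation power Φ(3.6/0.813 − 2.394) = 97.9%.

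**5. Success at any of the three looks.** The biopsy cohorts are separate patients: 30, 40 and 80, or 9, 12 and 24 per group after 10% loss. If 4% holds at every time point, power at each look is 57.2%, 74.4% and 98.1%, and overall power is 1 − (1 − 0.572)(1 − 0.744)(1 − 0.981) = 99.8%.

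**The case against.** The strongest reply is that nothing is miscalculated and little follows. Both printed figures are correct for their inputs. The sample size rests on NSAA, and no decision changes if dystrophin power is 98% and not above 99%. Section 11.3.2.1 cites discontinuation of 0.6% and 2.7% in previous pivotal studies, so 10% loss is pessimistic, and with no loss the Week 46 figure is 99.0%. Success may be declared at any of three looks, which restores about 99.8% if the effect is already 4% at Week 12. If 3 mg/kg were dropped before the Week 46 cohort began and allocation became 2:1, 24 vs 48 would give 99.8%. Section 11.1 discloses the t-test simplification, and one model fitted to biopsies from all three visits does, literally, use all biopsies.

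Most of this stands and limits the point to a minor one. It does not make 11.1 accurate: the statement is specifically about 46 weeks, and that test has neither 150 patients nor a two-sided 5% level.

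Three stronger readings are tempting, and the documents do not support them.

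- *The trial is underpowered for dystrophin.* It is not, at the assumed effect and full enrollment.
- *The NSAA 88% is a safe lower bound.* It is not. The control-based rule can bring the single-dose comparison to about 84%, and the pooled test falls below 88% if 3 mg/kg works clearly less well.
- *Power can be tabulated for particular stopping points.* The text supplied does not give the NSAA enrollment targets, so any total below 150 would be an assumption and would need its any-look counterpart. Dropping 3 mg/kg at exactly 30 or 70 randomized patients cannot be assumed either: interim results come at least 12 or 22 weeks after the relevant patients are randomized, and no enrollment pause is described.

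**Conclusion.** The power statements are wrong as descriptions of the planned tests, with minor consequence. Week 46 dystrophin power is about 98.1% at the stated 10% loss and 99.0% with none, against a claim of more than 99%. It would be lower if an NSAA interim ended enrollment early under 1:1:2:2. The NSAA 88% belongs to one dose against combined placebo with dropouts removed. The default pooled test has about 93% to 95%, given 3 points in both doses.

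These values assume the plan's own effects and SDs, equal SDs across arms, equal thirds in the Week 46 cohort, and t-tests in place of the Bayesian models. Borrowing from historical controls (NSAA) and from study WVE-DMDX51-002 (dystrophin) is not specified well enough here to quantify.

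**What to change.** In Section 11.1 and the synopsis:

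1. **Dystrophin.** Restate Week 46 power as about 98% (10% loss) to 99% (no loss) for 4.5 mg/kg against placebo, with up to 80 Week 46 biopsies under 1:1:2:2 at one-sided 0.00833. Say that it is lower if an NSAA interim stops enrollment before 150.
2. **NSAA.** Label 88% as one dose against combined placebo, 45 vs 45 with dropouts removed, and do not call it a minimum. Add the pooled-test power of about 93% to 95%, stating how dropouts are handled and that it is conditional on a 3-point effect in both doses.
3. **Biopsies.** In Section 4.1.2 and the synopsis, clarify that using all biopsies in the primary analysis does not mean that all of them inform the Week 46 effect.
4. **Approximation.** Say that the figures are t-test approximations to Bayesian analyses that also draw on external data.

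The cost is a few sentences and restated figures. Patients, visits, thresholds and analyses stay as they are. The one downside is a slightly less favourable Week 46 dystrophin figure.
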